8.10. Other aspects

Not applicable.

9. PROTECTION OF HUMAN SUBJECTS

9.1. Patient information

This study involves data that exist in anonymized structured format and contain no patient personal information.

9.2. Patient consent

As this study involves anonymized structured data, which according to applicable legal requirements do not contain data subject to privacy laws, obtaining informed consent from patients by Pfizer is not required.

9.3. Institutional review board (IRB)/Independent ethics committee (IEC)

IRB/IEC review is not required.

9.4. Ethical conduct of the study

The study will be conducted in accordance with legal and regulatory requirements, as well as with scientific purpose, value and rigor and follow generally accepted research practices described in Guidelines for Good Pharmacoepidemiology Practices (GPP) issued by the International Society for Pharmacoepidemiology (ISPE). This study will follow the Strengthening the Reporting of Observational Studies in Epidemiology (STROBE) reporting guideline

10. MANAGEMENT AND REPORTING OF ADVERSE EVENTS/ADVERSE REACTIONS

[figure not shown]
This study involves data that exist as structured data by the time of study start. In these data sources, individual patient data are not retrieved or validated, and it is not possible to link (i.e., identify a potential association between) a particular product and medical event for any individual. Thus, the minimum criteria for reporting an adverse event (AE) (i.e., identifiable patient, identifiable reporter, a suspect product, and event) cannot be met

11. PLANS FOR DISSEMINATING AND COMMUNICATING STUDY RESULTS

A final study report detailing the final study protocol and the analysis results will be provided when the study is complete.

In the event of any prohibition or restriction imposed (e.g., clinical hold) by an applicable competent authority in any area of the world, or if the investigator is aware of any new information which might influence the evaluation of the benefits and risks of a Pfizer product, Pfizer should be informed immediately.

[figure not shown]
[figure not shown]
PFIZER CONFIDENTIAL

ANNEX 1. LIST OF STAND ALONE DOCUMENTS

None

[figure not shown]
ANNEX 2. ENCEPP CHECKLIST FOR STUDY PROTOCOLS

N/A

ANNEX 3. ICD-10 CODE LIST

IC Condition	ICD-10 Code
HIV/AIDS*	B20-B24
Solid malignancy	
Organ/system malignant tumors	C00-C07; C11-C19; C22-C80; Z85
Neuroendocrine tumors	C7A; C7B; D3A
Neoplasms of uncertain behavior	D00-D49
Bone marrow transplant	Z94.81
Organ transplant	
Complications of transplanted organ	T86
Organ transplant status	Z94 except Z94.81; Z98.85
Rheumatologic or other inflammatory condition	
Sarcoidosis	D86
Amyloidosis Not Otherwise Specified (NOS)	E85
Familial Mediterranean fever	E85.0; M04
Amyloidosis Not Elsewhere Classified (NEC)	E85.1; E85.3; E85.8
Multiple sclerosis	G35
Other Central Nervous System (CNS) demyelination	G36; G37.1; G37.3; G37.8; G37.9
Acute infective polyneuritis	G61.0; G61.9
Acute myocarditis	I40
Polyarteritis nodosa and other	M30
Allergic alveolitis/pneumonitis NOS	T78.40; J67.9
Other alveolar pneumonopathy	J84.01; J84.02; J84.09

PFIZER CONFIDENTIAL

IC Condition	ICD-10 Code
Enteritis and colitis	K50-K52
Lupus erythematosus	L93.0; L93.2; M32
Diffuse connective tissue disease	L94; M35.8; M35.9
Arthropathy with infection	M12.9; M01.X0; M02.10
Crystal arthropathies	M11
Rheumatoid arthritis/inflammatory polyarthropathy	M05-M14
Inflammatory spondylopathies	M46
Polymyalgia rheumatica	M31.5; M35.3
Chronic inflammatory demyelinating polyneuropathy	G61.81
Immune thrombocytopenic purpura	D69.3
Primary Immunodeficiency	
X-linked agammaglobulinemia	D80.8
Common variable immunodeficiency	D83.1; D83.2; D83.8; D83.9
Immunoglobulin A (IgA) deficiency	D80.2
Immunoglobulin G (IgG) sub-class deficiency	D80.3
Severe combined immunodeficiency	D81.1
Di George syndrome	D82.1
Wiskott-Aldrich	D82.0
Ataxia telangiectasia	G11.3
Interferon-gamma/Interleukin 12 axis deficiencies	D84.89
Persistent complement, properdin or Factor B deficiency	D84.1
Received eculizumab for >14 days in the baseline period	
Chronic granulomatous disease	D71
Chediak-Higashi	E70.330
Leukocyte adhesion deficiency	D72: Genetic anomalies of leukocytes
Myeloperoxidase deficiency	D72.89: Other specific disorders of White Blood Cells (WBCs)

PFIZER CONFIDENTIAL

IC Condition	ICD-10 Code
Other immune conditions	
Disorders of immune mechanism	D89
Neutropenia	D70
Functional disorders of neutrophils	D71
Genetic anomalies of leukocytes	D72.0
Decreased leukocyte count	D72.81
Leukocyte disease NEC	D72.89
Leukocyte disease NOS	D72.9
Myelofibrosis	D75.81
Blood diseases NEC	D47.4; D75.89; D75.9; D89.2
Blood diseases NOS	D75.9; D75.89
Immunologic findings NEC	R76; R83.4-R87.4; R89.4
Nonspecific immune findings NEC and NOS	R76; R83.4-R87.4; R89.4
Sickle cell disease	D57
Asplenia	Q89.01
Psoriatic arthritis	L40.52
Kidney condition	
Chronic kidney disease	A18.11; A52.75; B52.0; C64.x; C68.9; D30.0x; D41.0x-D41.2x; D59.3; E08.2x; E09.2x; E10.2x; E10.65; E11.2x; E11.65; E13.2x; E74.8; I12.xx; I13.0; I13.1x; I13.2; K76.7; M10.3x; M32.14; M32.15; N01.x-N08.x; N13.1; N13.1x-N13.39; N14.x; N15.0; N15.8; N15.9; N16; N17.x; N18.1-N18.5; N18.8; N18.9; N19; N25.xx; N26.1; N26.9; O10.4xx; O12.xx; O26.83x; O90.89; Q61.02; Q61.1x-Q61.8; Q26.0-Q26.39; R94.4
End stage renal disease	N18.6 AND on dialysis (any type): Z99.2; Z49; Z9115; Z4931; OR Z4901
On hemodialysis	Any subject with the ESRD codes above and ≥ 1 hemodialysis procedure session during the baseline period identified by at ≥ 1 of the following codes: Z49.31;

IC Condition	ICD-10 Code
	Z49.32; I953; A4680; A4690; A4706- A4709; A4730; A4740; A4750; A4755; A4802; A4870; A4890; A4918; E1520; E1530; E1540; E1550; E1560; E1575; E1580; E1590; E1600; E1610; E1615; E1620; E1625; E1636; G0365; G0392; G0393; G8081; G8082; G8085; S9335; 90935; 90937; 90940; 93990; 36800; 36810; 36815
On peritoneal dialysis	Any subject with the ESRD codes above and ≥ 1 peritoneal dialysis procedure session during the baseline period identified by ≥ 1 of the following codes: Z49.02; 90945; 90947
Hematologic malignancy**	
Lymphatic and hematopoietic tissue malignancy	C81-C83; C88-C96

CNS: central nervous system; ICD-10: International Classification of Diseases, 10th Revision; IgG: Immunoglobulin G, IgA: Immunoglobulin A, NOS: not otherwise specified; NEC: necrotizing enterocolitis; WBCs: White blood cells.

*Excluded asymptomatic HIV code of ICD-10: Z21.

**Required to have usage of an immunosuppressive medication (chemotherapeutic agent, immunomodulator, or systemic corticosteroids) for >14 days anytime during the baseline period.

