8.2.1. Inclusion criteria

Patients must meet all of the following inclusion criteria to be eligible for inclusion in the study:

1. Unique enrollees in the HealthVerity Vaccine dataset any time **after** 10 December 2020
2. At least 12 years on the index date (ie, first vaccination date)
3. No evidence of prior COVID-19 infection (a medical claim, pharmacy claim, or chargemaster record with an International Classification of Diseases, 10th Revision, Clinical Modification (ICD-10-CM) diagnosis code of U07.1) in the 12 months prior to the index date
4. Have 12 months of continuous enrollment with medical benefits (with or without pharmacy benefits) prior to the index date

Subjects with an IC condition were identified via an algorithm originally developed and validated by Greenberg et al²⁴ for use in administrative claims database studies. For this study, this algorithm will be modified and expanded based on expert medical opinion. The algorithm is depicted in [Figure 1](#).

Subjects will be identified as immunocompromised if they had ≥ 1 hospitalization or ≥ 2 outpatient visits on separate dates with an ICD-10-CM code on a healthcare claim indicating an IC condition or if they had usage of specific immunosuppressive medications during the 12-month baseline period. The IC case definition will incorporate 8 groups based on clinical diagnoses only, 1 group based on both clinical diagnoses and usage of immunosuppressive medication, and 2 other groups based on usage of immunosuppressive medication only, for a total of 11 groups with an IC condition ([Figure 1](#)). Subjects with >1 IC condition will also be assessed, for a total of 12 mutually exclusive groups for inclusion in this study. The list of ICD-10-CM codes used to identify IC cases by diagnosis and list of immunosuppressive medications are shown in the Annex.

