This algorithm differs from that used in Greenberg et al²⁶ by the following modifications, considered relevant for COVID-19 based on expert medical opinion: the inclusion of subjects with a solid malignancy who had radiation therapy or any treatment mix; the separation of subjects with a bone marrow transplant and those with an organ transplant; the inclusion of chronic inflammatory demyelinating polyneuropathy and immune thrombocytopenic purpura in the “rheumatologic or other inflammatory condition” group; the inclusion of sickle cell disease, asplenia, and psoriatic arthritis in the “other immune disorders” group; the addition of subjects with primary immunodeficiencies and those with CKD or ESRD; the requirement that subjects with a hematologic malignancy have evidence of usage of an immunosuppressive medication; the reclassification of subjects with only usage of an immunosuppressive medication; the removal of subjects with usage of only low dose prednisone; and the inclusion of an ad-hoc group of subjects who had taken anti-metabolites. Additionally, the following subcategories will be created: the first 9 subject groups were stratified according to treatment status; organ transplant subjects will be stratified according to time of receipt of the first COVID-19 vaccine dose in relation to the date of transplant; and subjects with hematologic malignancy will be stratified by time of receipt of treatment relative to their 1st vaccine dose.

When categorizing subjects with the different types of IC conditions, all the subject groups will be mutually exclusive. Subjects meeting the criteria for classification into only a single IC group will be classified accordingly into subject groups 1-11. Any subjects meeting the criteria for classification into multiple IC groups will be categorized into the >1 IC condition group (12th subject group).

All subjects will be grouped into an overall study population consisting of subjects identified as having an IC condition or not (i.e., non-IC). Subjects with an IC condition will be further categorized into the specific IC condition groups.

Figure 1: Algorithm to define immunocompromising conditions

Algorithm for case definitions of IC conditions in HealthVerity US claims database

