8.3. Variables

Table 1. Immunocompromising Conditions definition

Variable	Role	Data source(s)	Operational definition
Immunocompromising Conditions	Cohort Definition	HealthVerity Vaccine Data	
Subjects will be categorized into the following 12 mutually exclusive IC groups based on the algorithm detailed in Figure 1:
 
Symptomatic HIV/AIDS, solid malignancy, bone marrow transplant recipients, organ transplant recipients, rheumatologic or other inflammatory conditions, primary immunodeficiencies, other intrinsic immune conditions, chronic kidney disease or end stage renal disease, hematologic malignancy, immunosuppressive treatment only, antimetabolites only, or >1 IC condition.

PFIZER CONFIDENTIAL

Table 1. Immunocompromising Conditions definition

Variable	Role	Data source(s)	Operational definition
			
Subjects falling into more than one of these categories will be categorized as having >1 IC condition.
 
At a minimum, subjects will be required to have one inpatient claim or two outpatient claims on separate days with the IC condition of interest in the baseline period. In cases when >14 days of treatment are required it will be based on the dispensed day supply or distinct days of treatment in the baseline period.
 
The main diagnosis codes to identify IC conditions are presented in ANNEX 1. LIST OF STAND ALONE DOCUMENTS.

Table 2. Vaccination Status definitions

Variable	Role	Data source(s)	Operational definition
Any vaccination	Cohort Definition	HealthVerity Vaccine Data	
Patients with a claim for any vaccine will be considered vaccinated with any vaccine based on the following codes:
 
Pfizer/BioNTech: 91300, 0001A, 0002A, 59267100001, 59267100002, 59267100003
 
Moderna: 91301, 0011A, 0012A, 80777027310, 80777027399, 80777027315, 80777027398
 
Johnson & Johnson: 91303, 0031A, 59676058005, 59676058015
 
Source: https://www.cdc.gov/vaccines/programs/iis/COVID-19-related-codes.html

Fully Vaccinated	Cohort Definition	HealthVerity Vaccine Data	
Patients will be considered fully vaccinated if they meet any of the following definitions:
 
Two claims for Pfizer/BioNTech vaccine on separate days with >14 days of follow-up after the 2nd vaccination date. No claims for any other vaccines are allowed.

PFIZER CONFIDENTIAL

Table 2. Vaccination Status definitions

Variable	Role	Data source(s)	Operational definition

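### Annex 3 lets the personal-history code Z85 qualify a subject as solid malignancy, so untreated cancer survivors, including those with past leukemia or lymphoma, enter the IC cohort

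*Combined protocol and SAP*

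**What the plan says.** Annex 3, under solid malignancy, gives the codes for organ and system tumors as "C00-C07; C11-C19; C22-C80; Z85". Z85 carries no subcode restriction, footnote or recency condition. The hematologic malignancy row lists "C81-C83; C88-C96", with the footnote "Required to have usage of an immunosuppressive medication (chemotherapeutic agent, immunomodulator, or systemic corticosteroids) for >14 days anytime during the baseline period".

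Section 8.2.1 sets the entry rule: at least "1 hospitalization or ≥ 2 outpatient visits on separate dates with an ICD-10-CM code on a healthcare claim indicating an IC condition", or use of specified immunosuppressive drugs. It describes the groups as "8 groups based on clinical diagnoses only, 1 group based on both clinical diagnoses and usage of immunosuppressive medication", plus two medication-only groups. Solid malignancy is one of the eight. Treatment status and treatment type divide that group into strata but are not conditions of entry. The same section lists, among its deliberate changes to the source algorithm, "the requirement that subjects with a hematologic malignancy have evidence of usage of an immunosuppressive medication". Subjects who meet more than one group go to the >1 IC condition group.

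Table 1 in section 8.3 repeats the minimum claim count: "one inpatient claim or two outpatient claims on separate days with the IC condition of interest in the baseline period".

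**The concern.** A history code is used when a cancer is in the past, yet here it qualifies a subject on the same footing as an active-tumor code. Two things follow.

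First, people whose immune function may be ordinary are counted as immunocompromised. IC status defines the Aim 2 breakthrough rate, the risk difference between IC and non-IC in section 8.7, and the condition subgroups. The rationale in section 6 is to learn which conditions reduce effectiveness, and diluting one condition group works against that.

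Second, Z85 cuts across the sponsor's own hematologic rule. That rule keeps untreated hematologic malignancy out of its group, but the history subcodes for leukemia (Z85.6) and for lymphoma and related neoplasms (Z85.7) bring untreated past disease into the IC cohort under a different disease label.

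**Working it through.** The plan states no figure to reproduce here. The check applies its entry rules to its code lists and then shows the scale under stated assumptions.

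**Classification.** Inputs are the Annex 3 lists, the claim-count rule and the multiple-group rule in section 8.2.1. Each case is assumed to meet no other IC criterion.

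| Case | Baseline record | Result under the plan |
|---|---|---|
| A | Past solid tumor; Z85 at two outpatient visits on separate dates; no drugs | IC, solid malignancy |
| B | Past lymphoma; Z85.7 at two such visits; no drugs | IC, solid malignancy |
| C | Active lymphoma; C83 at two such visits; no drugs | Fails the hematologic group; non-IC |
| D | C83 with more than 14 days of qualifying drug, and Z85 also meeting the claim count | >1 IC condition instead of hematologic malignancy |

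B and C together show the conflict: history qualifies where active disease does not. D remains IC and only the subgroup is wrong. It needs Z85 on one hospitalization or two outpatient visits, so a single outpatient mention does not trigger it. The same move applies to a subject in any other IC group who also meets the count on Z85.

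**Scale in the solid malignancy group.** Let R be the true rate ratio against non-IC for members who qualify without Z85, and f the share of the group's person-time from Z85-only subjects. Assume Z85-only subjects have the non-IC rate. Then

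observed ratio = (1 − f)R + f = 1 + (R − 1)(1 − f).

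| f (assumed) | R = 2.0 | R = 3.0 |
|---|---|---|
| 20% | 1 + 1 × 0.8 = 1.8 | 1 + 2 × 0.8 = 2.6 |
| 40% | 1 + 1 × 0.6 = 1.6 | 1 + 2 × 0.6 = 2.2 |
| 60% | 1 + 1 × 0.4 = 1.4 | 1 + 2 × 0.4 = 1.8 |

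The rate difference is multiplied by the same (1 − f). If Z85-only subjects instead have k times the non-IC rate, the ratio falls by f(R − k), which is smaller for k between 1 and R and zero at k = R.

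**Pooled IC cohort.** If solid malignancy contributes a share s of all IC person-time, the diluting share is s × f, which is less than f because s is below 1. The documents give neither s nor f, so I attach no pooled figure.

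**The case against.** The strongest reply is that the plan already separates treated from untreated subjects in every diagnosis-only group and splits solid malignancy by treatment type, so untreated survivors would sit in the untreated stratum, where the dilution could be seen. This stands in part. The strata expose some of the problem, but the untreated stratum mixes survivors with untreated active cancer. A survivor given more than 14 days of an immunosuppressive drug for another reason lands in the treated stratum. The pooled IC result is not corrected at all.

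Other safeguards are general. Section 8.7 plans to vary the IC case definition without naming Z85, and section 8.9 concedes that the accuracy of the modified algorithm cannot be assessed. Z85 may be inherited from a source algorithm, because section 8.2.1 does not list it as a change; that cannot be checked here. Even so, the added hematologic rule creates the conflict between cases B and C. The annex writes exceptions where it wants them, as for Z94.81 and for asymptomatic HIV (Z21).

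Two limits on the evidence remain. The meaning of Z85 comes from ICD-10-CM and not from protocol text. Figure 1 is not shown and could contain a treatment condition, although the text of section 8.2.1 points the other way.

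A reader might infer that a treated lymphoma patient who also carries Z85 has no IC condition of interest. The documents do not support that: such a patient meets the hematologic definition. A reader might also apply the illustrated ratios to the primary IC versus non-IC contrast, but they describe one group of twelve.

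**Conclusion.** The concern holds. As written, a personal-history code alone admits untreated survivors to the IC cohort as solid malignancy. Untreated past leukemia or lymphoma enters by that route, while untreated active hematologic disease does not qualify through its own group. Subjects who meet another group and also the Z85 claim count are misrouted to >1 IC condition but stay in the cohort.

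The direction of bias is toward no difference, provided that Z85-only subjects have a breakthrough rate near the non-IC rate; nothing in the documents establishes that rate. The size is unknown. The fall from 2.0 to between 1.8 and 1.4 rests on an assumed 20% to 60% Z85-only share and an assumed true ratio, for the solid malignancy group only. The proportional effect on the pooled IC contrast is smaller. This should be changed before the main results are produced.

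**What to change.** Remove Z85 from the primary solid malignancy definition. Z85-only subjects then count as IC only if they qualify through another listed code or group. State also that Z85 no longer counts as an IC diagnosis when the medication-only groups or the >1 IC condition group are assigned. Report Z85-only subjects in a separate descriptive row, and prespecify a sensitivity analysis that adds them back for the solid malignancy rate, the pooled IC rate and the risk difference.

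This does not turn solid malignancy into a group defined by active malignant codes alone, as a reader might infer, because D00-D49 stays on the list.

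The cost is one code deletion and one additional run on existing data. The downside is a smaller group and the loss of some active disease miscoded as history; the sensitivity run would show how much the results depend on that.

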Eight of the disease groups will include subjects with 1) symptomatic human immunodeficiency virus (HIV)/acquired immunodeficiency syndrome (AIDS); 2) solid malignancy; 3) bone marrow transplant; 4) organ transplant (excluding bone marrow); 5) rheumatologic or other inflammatory condition; 6) a primary immunodeficiency; 7) other immune conditions; and 8) chronic kidney disease (CKD) or end stage renal disease (ESRD). Subjects in these IC groups (shown as “Group 1” in [Figure 1](#)) will be further stratified by treatment status: those with usage of immunosuppressive medications for >14 days anytime during the baseline period and those without any evidence of >14 days of usage of an immunosuppressive medication during the baseline period. Subjects with a bone marrow or

organ transplant will be further stratified by those who received their 1st vaccine dose >100 days prior to their transplant and those who received it <100 days prior to their transplant. Subjects with a solid malignancy will be further stratified by their treatment type: chemotherapy or radiation therapy or immunomodulator, or a mix of these treatments.

The 9th subject group (shown as “Group 2” in [Figure 1](#)) will include those with a hematologic malignancy, required to have usage of an immunosuppressive medication (chemotherapeutic agent, immunomodulator, or systemic corticosteroid) for >14 days anytime during the baseline period; this subject group will be further stratified by their use of an immunosuppressive medication >6 months or ≤ 6 months prior to their index date.

The 10th subject group will include subjects with usage of an immunosuppressive medication (chemotherapeutic agent, immunomodulator, or systemic corticosteroid excluding low-dose [<60mg/day] prednisone) for >14 days anytime during the baseline period, but without any ICD-10-CM diagnosis codes indicating the above listed IC conditions on a healthcare claim anytime during the baseline period. Subjects with >14 days usage of antimetabolites anytime during the baseline period will be excluded from this subject group and placed in the 11th subject group.

[figure not shown]

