8.7. Data analysis

Data analyses will follow extensive feasibility analyses aimed at determining whether a full study and the assessment of vaccine effectiveness are feasible, as illustrated below:

Study implementation approach

Characteristics of the IC, non-IC and total population (IC + non-IC) groups will be described. Descriptive statistics for continuous variables will include N (number of patients), mean, median, standard deviation, Q1, Q3, minimum, and maximum. Categorical variables will be described using frequency counts and percentages.

The incidence rate of breakthrough cases of SARS-CoV-2 infection will be determined based on the following:

- Among fully vaccinated patients, those who have a claim for COVID-19 (ICD-10-CM: U07.1) that occurs on or after >14 days following their second dose of an mRNA vaccine (or 1st dose of Johnson & Johnson) will be considered to have had a breakthrough event. The time from 14 days after the qualifying dose until the breakthrough event will be the person time at risk.

PFIZER CONFIDENTIAL

- Among fully vaccinated patients with no evidence of COVID-19 after their qualifying dose, the time from 14 days after the qualifying dose until the end of follow-up will be the person time at risk.

[figure not shown]
The incidence rate of breakthrough cases of SARS-CoV-2 infection will be calculated as the number of patients who experience the event divided by the observed time at risk, and reported per 100 person years. Poisson 95% confidence intervals will be reported for the incidence rates.

Absolute effect measures such as risk difference between non-IC and IC will be reported. Time period specific effect estimates (eg, at 6 months after vaccination) may be estimated if feasible. The characteristics of the breakthrough infections will be described, including clinical presentation and severity.

The primary analysis will describe results among the non-IC cohort and the IC cohort who are vaccinated with BNT162b2. Subgroup analyses will include results for clinically meaningful subgroups as defined by vaccination type, relevant patient characteristics (eg, age), and each IC condition as listed below:

- HIV/AIDS
- Solid malignancy
- Bone marrow transplant
- Organ transplant (excluding bone marrow)
- Rheumatologic/inflammatory
- Primary Immunodeficiencies
- Other immune condition
- CKD or ESRD
- Hematologic malignancy

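### Annex 3 counts every D00-D49 code as solid malignancy with no treatment required, so subjects with neither a malignant code nor immunosuppressive use enter the pooled IC cohort

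*Combined protocol and SAP*

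**What the plan says.** Annex 3 has three rows under solid malignancy: organ or system malignant tumors (C ranges plus Z85), neuroendocrine tumors (C7A, C7B, D3A), and "Neoplasms of uncertain behavior", coded as D00-D49 without exclusions.

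On entry, section 8.2.1 states: "The IC case definition will incorporate 8 groups based on clinical diagnoses only". Solid malignancy is the second of these eight. The claims threshold is "≥ 1 hospitalization or ≥ 2 outpatient visits on separate dates with an ICD-10-CM code on a healthcare claim" in the 12-month baseline. The eight groups are then stratified by treatment, and one stratum is "those without any evidence of >14 days of usage of an immunosuppressive medication during the baseline period".

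Hematologic malignancy is handled differently. The Annex 3 footnote reads "Required to have usage of an immunosuppressive medication", for more than 14 days in the baseline period.

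Section 8.7 sets the use of the cohorts: "The primary analysis will describe results among the non-IC cohort and the IC cohort who are vaccinated with BNT162b2", and "Absolute effect measures such as risk difference between non-IC and IC will be reported". The same section plans a screening-method VE for the IC population overall and by IC group. It mentions the IC case definition as one example of what sensitivity analyses may vary, without specifying an alternative definition.

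**The concern.** By its own label, the D00-D49 row does not describe established malignancy. Annex 3 also treats parts of the range as something else: D30.0x and D41.0x-D41.2x appear in the chronic kidney disease list, and D47.4 appears among blood diseases under other immune conditions. Because entry is by diagnosis alone, a subject with two outpatient visits for such a code, no malignant code and no immunosuppressive treatment is IC for every pooled analysis.

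What is at stake is the meaning of the pooled IC result. The breakthrough rate (Aim 2), the risk difference against non-IC and the overall IC VE would each average over people whom the label does not describe as having cancer and whom treatment has not made immunocompromised. If their breakthrough rate is lower than that of other IC subjects, the reported excess is too small.

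The double listing of codes is a separate fault. It affects the group for more than one IC condition, which has its own subgroup results and its own VE.

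**Working it through.** **Step 1: who enters.** Setting the texts side by side:

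| Element | Solid malignancy through D00-D49 | Hematologic malignancy |
|---|---|---|
| Code row | D00-D49, labelled as uncertain behavior | C81-C83; C88-C96 |
| Claims threshold | 1 hospitalization or 2 outpatient visits | same |
| More than 14 days of immunosuppressive use | not required; used to stratify | required |

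The plan states no sample size, expected rate or effect size (section 8.5 declines a formal computation), so it has no figure to reproduce.

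**Step 2: effect on the IC versus non-IC difference.** Let R0 be the non-IC rate and R0 + D the rate in IC subjects who qualify by another route. Let f be the share of the IC cohort that enters only by an untreated D00-D49 code (share of person-time for rates, of subjects for risks). Let that subgroup's rate be R0 + k*D. Then

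pooled IC rate = (1-f)(R0 + D) + f(R0 + k*D) = R0 + D[(1-f) + f*k],

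so the fraction of D that remains is (1-f) + f*k.

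Neither f nor k is in the documents. The values below are assumed, only to show how the expression behaves:

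| f | k = 0 | k = 0.5 | k = 1 | k = 1.5 |
|---|---|---|---|---|
| 10% | 0.90 | 0.95 | 1.00 | 1.05 |
| 30% | 0.70 | 0.85 | 1.00 | 1.15 |
| 50% | 0.50 | 0.75 | 1.00 | 1.25 |

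For example, f = 30% and k = 0.5 give 0.70 + 0.15 = 0.85. The difference shrinks for every k below 1, is unchanged at k = 1 and grows above 1. The planned rates are crude, so k reflects recorded U07.1 claims. Age, testing and care-seeking in this subgroup enter it as well as immune status.

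**Step 3: doubly listed codes.** Under section 8.2.1, anyone meeting the criteria for several groups goes to the 12th group.

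| Code | Within solid malignancy | Also listed under |
|---|---|---|
| D30.0x; D41.0x-D41.2x | D00-D49 | chronic kidney disease |
| D47.4 | D00-D49 | other immune conditions |
| C64.x; C68.9 | C22-C80 | chronic kidney disease |

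Two outpatient visits with one of these codes satisfy both lists, so a single diagnosis becomes more than one IC condition. This does not alter the pooled IC cohort under the present lists, because the subject is IC under either. It alters the 12th group and the single-condition groups from which such subjects are removed.

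**The case against.** The strongest reply is that entry without treatment is less settled than it looks. Section 8.2.1 splits solid malignancy by chemotherapy, radiation, immunomodulator or a mix, with no untreated category. It also describes one modification as including solid malignancy subjects who had radiation or any treatment mix. Figure 1, which depicts the algorithm, is not available here. Against that, the same section says outright that the group is diagnosis-only and keeps a stratum without immunosuppressive use, and this is the text an analyst would follow.

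Second, the contrast with hematologic malignancy proves little alone. None of the eight diagnosis-only groups requires treatment, and the hematologic rule is a disclosed exception. The case rests on the mismatch between label and range, combined with diagnosis-only entry.

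Third, there is partial mitigation. Solid malignancy is reported separately and split by immunosuppressive use, the IC case definition is a possible sensitivity analysis, and the study is mainly descriptive. This makes the problem visible within the subgroup. It does not protect the pooled IC result, and no analysis without D00-D49 is committed.

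A reader might also infer that section 8.9 concedes the point by saying that the effect of the modifications on accuracy cannot be assessed. It does not. Section 8.2.1 lists the modifications and D00-D49 is not among them, so the range may be inherited from the source algorithm. Nor does the quoted specificity of 97.6% defend the range here, since the reference list shows that the validation was in patients with severe sepsis.

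**Conclusion.** The point holds as a definitional fault with a cheap remedy. As written, the plan places subjects with neither a malignant code nor more than 14 days of immunosuppressive use in the pooled IC cohort, and its existing subgroup and sensitivity provisions leave that cohort unchanged.

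Its size is unknown. The fraction of the difference that remains is (1-f)+f*k, and the documents supply neither quantity. A reader might infer that the study will understate the IC excess, or that a given rate ratio would fall by a given amount. The documents do not support either reading. Shrinkage assumes that these subjects' recorded breakthrough rate is below that of other IC subjects, which age, testing or care-seeking could offset. Section 8.7 names a risk difference, not a rate ratio, as its example of the planned contrast.

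The double listing needs no such assumption. It follows from the lists and the 12th-group rule, but it concerns classification within IC and is not evidence of dilution.

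**What to change.** 1. Reconcile D00-D49 with its label in Annex 3: either restrict the range to what the label describes, or relabel it and justify the full range.
2. In the primary analysis, put subjects who qualify only through D00-D49 and have no more than 14 days of immunosuppressive use in a separate row, counted neither as IC nor as non-IC, and report their number. Those with more than 14 days of such use and no other IC diagnosis go to the drug-use groups (10 or 11) under those groups' existing definitions.
3. Leave Z85 as listed, and state explicitly whether D3A stays under neuroendocrine tumors.
4. In section 8.7, name the present broad definition as the IC case definition sensitivity analysis, applied to the rate, the risk difference and VE.
5. State that one code listed under two groups does not by itself make more than one IC condition, and assign each such code to one group (at least D30.0x, D41.0x-D41.2x, D47.4, C64.x and C68.9). Do this before step 2, because the assignment decides who qualifies only through D00-D49.

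The cost is an Annex 3 edit, one extra row and one named sensitivity analysis. The data already exist, so collection does not change. The downside is a smaller IC cohort and less comparability with the source algorithm, which the sensitivity analysis preserves. The reported count would also supply the head-count share that is missing now.
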